The sample size has been assessed on the basis of the following rules and assumptions:

- 1. Statistical provisions.
 - 1.1 the power of the statistical tests " $P = (1 \beta)$ " is assumed to be 80% (the probability of correct rejection of the null hypothesis is 0.8);
 - 1.2 the probability of a type I error " α " is allowed to be less than 5% (the probability of the erroneous acceptance of an alternative hypothesis is less than 0.05);
 - 1.3 the statistical tests are 2-sided;
 - 1.4 the calculation of the sample size is based on the assumptions about the expected effects, declared in the primary efficacy endpoint of the Protocol;
 - 1.5 the ratio between the sample sizes of Rengalin and Placebo groups is 1:1 (1 Rengalin patient - 1 Placebo patient);
 - 1.6 statistical null and alternative hypotheses using the applied dosing regimen are formulated as follows:

H₀: p₁=p₂

$H_a: p_1 \!\!>\!\! p_2,$

where p_1 – proportion of subjects in Product group with improvement ≥ 1 ;

 \mathbf{p}_2 – proportion of subjects in Placebo group with improvement ≥ 1 ;

1.7 the calculation of sample size for statistical criteria will be made using the formula:

2.
$$n_1 = kn_2$$

$$\mathbf{n}_{2} = \frac{\left(\frac{z_{\alpha}}{2} + z_{\beta}\right)^{2}}{\epsilon^{2}} \left[\frac{p_{1}(1-p_{1})}{k} + p_{2}(1-p_{2})\right]$$

where $\mathbf{n_1}$, $\mathbf{n_2}$ – sample size in Rengalin and Placebo groups;

 $\boldsymbol{\epsilon}$ – expected difference between proportions of subjects with

improvement in Rengalin and Placebo groups;

k – sample size ratio (in this study equal to 1);

⁴ Holder of license: OOO "NPF "Materia Medica Holding", No. 70100045.

 $z_{\alpha/2}$ – tabular value of two-sided z-test for α ;

 z_{β} – tabular value for one-sided z-test for β ;

1.8 the final sample size will be determined using the formula:

$N_T = N_{PP} / (1 - C_w),$

where N_T – final sample size;

 N_{PP} – result of calculation in cl. 1.7, i.e. the scheduled number of the subjects completing the study per protocol;

 C_w – withdrawal coefficient.

2. Assumptions on expected clinical study effects: difference between proportion of the subjects with improvement (relative to visit 1) in product group and proportion of the subjects with improvement (relative to visit 1) in placebo group will be at least 0.2; conservative approach to evaluation of sample size will be applied⁵.

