Therefore, sample size will be **95** patients in each group (Rengalin and Placebo) to estimate superiority of the study drug over placebo.

Given potential withdrawal of at least 20% subjects during the study for various reasons, at least 238 subjects will be required to sign informed consent (119 per group).

Statistical criteria

All statistical calculations will be performed using two groups of statistical criteria:

- parametric to evaluate continuous and interval random variables;
- non-parametric for:
 - assessments of equality / inequality in the proportion of patients when compared for different visits,
 - analysis of frequencies of the compared variables,
 - assessment of continuous and interval random variables in case of violation of the normality assumption.

Parametric criteria

The application of parametric criteria will be accompanied by a check for normality of the compared samples (Kolmogorov-Smirnov test).

The following parametric methods and approaches are to be used:

• To assess the differences of continuous variables obtained in two different (independent) groups – Student t-test for independent samples.

⁵ The highest potential sample size at this effect size.

- To assess the dynamics of the compared indicators analysis of variance (ANOVA) or covariance (ANCOVA) in the modification with repeated measures.
- In case of multiple comparisons between the groups will apply a variety of corrections for multiplicity Dunnett, Tukey, Scheffe, Holm adaptive test, etc.
- In case of abnormal data distribution, approaches with the Generalized Linear Models and / or Mixed Linear Models will be used.
- Selection of the type of distribution, clarification of the factor and covariance structures of the model is carried out with fit statistics such as AIC (Akaike information criterion).

To perform the above-mentioned statistical tests and techniques, it is assumed that the following SAS procedures are used:

- UNIVARIATE check for normality of the compared distributions;
- CORR, MEANS calculation of descriptive statistics;
- TTEST Student t-test with all the modifications;
- GLM analysis of Generalized Linear Models for studying temporal dynamics (ANOVA, ANCOVA);
- GENMOD analysis of Generalized Linear Models.
- MIXED analysis of Generalized Linear Models.

Non-parametric criteria

Below, there are the main types of possible comparisons with the respective criteria:

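### For the score and continuous secondary endpoints, non-normality triggers two unranked fallback analyses, and the handling of baseline is left open, so the plan does not fix one p-value

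*Combined protocol and SAP*

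**What the plan says.** All of this is in the combined protocol and SAP, under Statistical criteria.

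- The opening list of uses for non-parametric methods includes "assessment of continuous and interval random variables in case of violation of the normality assumption".
- Parametric criteria begins: "The application of parametric criteria will be accompanied by a check for normality of the compared samples (Kolmogorov-Smirnov test". No significance level is given for this check.
- The same subsection lists a t-test for independent groups and, for change over time, repeated-measures ANOVA or ANCOVA, without choosing between them. It then says "In case of abnormal data distribution, approaches with the Generalized Linear Models and / or Mixed Linear Models will be used".
- On building those models, after mentioning the type of distribution: "clarification of the factor and covariance structures of the model is carried out with fit statistics such as AIC". No candidate list, compulsory baseline covariate or blinded selection step is given.
- The list of SAS procedures includes "MIXED analysis of Generalized Linear Models", and describes GLM in the same terms.
- Non-parametric criteria names the Friedman test for change over time. Mann-Whitney appears only as a SAS procedure.

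No method is tied to a named continuous endpoint. Under Endpoints, TCSS severity and cough monitoring are to be compared with baseline, while the CAT endpoint does not mention baseline.

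**The concern.** The same finding, non-normal data, leads to two families of analysis with no order between them, and the model family is itself an and/or. Two analysts who both follow the text can test different things and reach different conclusions from the same data. A linear mixed model also assumes normal residuals, so it is not in itself an answer to non-normality.

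The outcome variable is open as well. A rank test on Week 4 scores, a repeated-measures test and an ANCOVA treat baseline in three different ways, and all three can be read out of the text. TCSS severity is the first-listed secondary endpoint, so the choice matters for how the trial is read even though the primary result is untouched.

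**Working it through.** **1. The plan's own figure.** Evaluation of sample size sets 80% power, 5% type I error and a difference of 0.2, and states that "the statistical tests are 2-sided". The footnote asks for the largest sample at that difference, read here as 0.6 versus 0.4. With the plan's formula:

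n = (1.960 + 0.842)² / 0.2² × (0.6 × 0.4 + 0.4 × 0.6) = 7.849 / 0.04 × 0.48 = 94.19, so 95 per group.

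With 20% withdrawal, 95 / 0.8 = 118.75, so 119 per group and 238 in total. The stated figures reproduce. They concern the primary proportion, and nothing below changes them.

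**2. Would the normality check fail?** The documents give no SD, so SD 1 to 3 is assumed. Scores are simulated as rounded normals cut to the range 0-12, with baseline at least 2 as the inclusion criteria require. The check is taken at 5%, which is also an assumption.

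| Data, n = 95 | KS, estimated mean and SD | Plain KS critical values |
|---|---|---|
| TCSS visit scores | 94% to 100% reject | 10% to 100% |
| TCSS change scores | 77% to 100% | 4% to 100% |
| Wider whole-number scale (assumed 0-40, SD 5 to 8) | 15% to 30% | under 1% |

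The first column is the relevant one if UNIVARIATE, the procedure named in the plan, estimates the parameters.

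**3. What does a free choice of route cost?** Assumptions: no drug effect, 95 per arm, complete data, SD 2 or 2.2, baseline-to-Week-4 correlation 0.3 to 0.7. Each entry is the chance that at least one of the two tests has p < 0.05.

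| Pair of analyses | Either significant |
|---|---|
| Mann-Whitney on Week 4, or ANCOVA | about 7-8% |
| Mann-Whitney on Week 4, or AIC-chosen GLM | 6.7% to 7.5% |
| Mann-Whitney on Week 4, or change score (arm-by-visit) | 7.5% to 9.8% across simulation sets |
| t-test on Week 4, or t-test on change (no fallback used) | 7.9% to 9.4% |
| Mann-Whitney on change, or t-test on change | 5.5% to 5.9% |
| One fixed ANCOVA | 4.7% to 5.1% |

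Two independent 5% tests would give 1 − 0.95² = 9.75%, so the third and fourth rows are close to having two separate tests. The reason is baseline. With equal variances and correlation r, the correlation between Week 4 and change is √((1 − r)/2), which is 0.5 at r = 0.5. Between Week 4 and the baseline-adjusted score it is √(1 − r²) = 0.87.

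**4. Disagreement when there is an effect.** At an assumed mean shift of −0.85 (SD 2.2, correlation 0.4 to 0.6):

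- Mann-Whitney on Week 4 and the change-score test give different verdicts in 24% to 28% of trials.
- t-tests on Week 4 and on change differ in 23.6% to 26.4%, with no fallback involved.
- Rank test and t-test on the same change variable differ in 4.1% to 5.8%.

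**5. AIC selection on its own.** Type I error after AIC choice of distribution was 4.7% to 5.4%, and after AIC choice of covariates 4.9% to 5.3%.

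**The case against.** Much of the case on the other side stands.

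- *Scope.* A reader might infer that the main result, or every secondary p-value, is unstable. The primary endpoint and secondary endpoints 2 and 4 are proportions and go to frequency tests. Only TCSS severity, CAT and the cough monitoring done at one site are exposed.
- *Cause.* A reader might attribute the 9-10% to the clash between rank tests and models. It is not that: two t-tests with different baseline handling give nearly the same figure, and rank versus t-test on one variable adds less than 1 point to the nominal 5%. Deleting the normality check alone would not cure it.
- *AIC.* A reader might infer that AIC selection inflates the error rate. The simulations do not show that. It leaves the model unspecified, which is a lesser complaint. An objection that AIC cannot compare fixed factors under REML would need an estimation method that the plan does not state.
- *The check.* A reader might infer that it always fails. That depends on estimated parameters, visit scores and an assumed SD.
- *Conduct.* A reader might infer that the more favourable result will be reported. The documents describe no such practice. The figures show what a free choice would allow.
- *Labels.* The description of MIXED may be a translation slip, since the bullet quoted for the fallback says mixed linear models correctly. GENMOD, also listed, does handle non-normal distributions.

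What remains is that the two instructions share one trigger, neither outranks the other, and Non-parametric criteria does not settle the matter.

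**Conclusion.** The point holds in limited form. For TCSS severity, CAT and 24-hour cough monitoring, the plan gives conflicting instructions under non-normality and leaves the outcome variable open. For TCSS the conflicting branch is probably the one that will be reached; for CAT and cough monitoring this is less certain.

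If the route were chosen after seeing results, type I error would be about 2 to 3 points above nominal for Mann-Whitney on Week 4 or ANCOVA, and up to 4 to 5 points for Mann-Whitney on Week 4 or a change-score test. Most of the latter is due to baseline handling.

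These sizes rest on assumed SDs, correlations, score range and complete data, none of which the documents supply. The textual conflict does not depend on them. This should be corrected, but it does not threaten the primary analysis.

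**What to change.** Before unblinding:

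1. Delete the normality condition and the AIC selection of factors and distribution.
2. Name one between-arm analysis, with its outcome variable, for each continuous endpoint, to be used whatever the distribution. For TCSS and CAT, an example is ANCOVA of the Week 4 score on treatment and baseline value. At 95 to 119 per arm, a comparison of means does not need normal raw scores.
3. For cough monitoring, done at one site with no stated number of patients, that large-sample argument may not apply. State its model or transformation in advance as well.
4. Keep rank-based tests as labelled sensitivity analyses.
5. Correct the descriptions of MIXED (linear mixed models) and GLM (general linear models).

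The cost is wording and the loss of freedom to change model after seeing the data; the sample size stays at 238. There is also a likely gain. At the assumed shift of −0.85 and correlations of 0.4 to 0.6, ANCOVA had 80% to 91% simulated power, against about 73% to 74% for Mann-Whitney on raw Week 4 scores.

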Multicenter Double-Blind Placebo-Controlled Parallel-Group Randomized Clinical Trial of Efficacy and Safety of Rengalin in the Treatment of Cough in Patients with Chronic Obstructive Pulmonary Disease

Phase IV

Sponsor

OOO «NPF «MATERIA MEDICA HOLDING»

Protocol numberMMH-RN-005Version date:October 17, 2016ClinicalTrials.gov Id:NCT03159091

Protocol Summary

This document represents the protocol summary for the study on human subjects. The study will be carried out in accordance with ICH GCP, National Standard of the Russian Federation GOST 52379-2005 "Good Clinical Practice", Helsinki Declaration of World Medical Association, relevant requirements of the regulatory authorities as well as the study procedures.

Title of Study

Multicenter double-blind placebo-controlled parallel-group randomized clinical trial of efficacy and safety of Rengalin in the treatment of Cough in patients with chronic obstructive pulmonary disease.

Phase: IV

Sponsor: OOO "NPF "Materia Medica Holding", Moscow, Russia *Protocol No.* MMH-RN-005

Objective of the study

• To obtain additional data on the efficacy and safety of Rengalin in the treatment of cough in patients with stable chronic obstructive pulmonary disease (COPD).

Endpoints

Primary endpoint

 Percentage of patients with a positive response after 4 weeks of the treatment (response criterion is the reducing of the Total Cough Severity Score (TCSS)* by ≥1 compared to baseline).

* according to the 12-point of the Cough Severity Scale.

Secondary endpoints

- 1. Severity of cough (TCSS according to the Cough Severity Scale) after 4 weeks of the treatment compared to baseline.
- Percentage of patients with ≥50% lesser cough severity (according to TCSS) after 4 weeks of the treatment.
- 3. The severity of the clinical symptoms of COPD (according to COPD Assessment Test [CAT]) after 4 weeks of the treatment.
- 4. Percentage of patients with no exacerbation of COPD¹ within 4 weeks of the treatment.

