Body weight measurement	+	
Measurement of body length/height	+	

	17-Oct-2016	
Procedure/day	Visit 1 (Day 1)	Visit 2 (Week 4±3 days)
Body mass index calculation	+	
Evaluation of cough severity (according to Cough Severity Scale)	+	+
Evaluation of COPD impact on the subject's life (CAT)	+	+
Pregnancy test	+	
Concomitant therapy	+	+
Computer spirometry* (evaluation of FEV1/FVC and post-bronchodilator FEV1)	+	
Eligibility assessment	+	
Randomization and prescription of study drug	+	
Study drug supply	+	
Study drug accountability, compliance assessment		+
Evaluation of treatment safety	+	+
24-hour cough monitoring**	+ **	+ **

* Where spirometry cannot be performed, spirometry parameters dating no more than 3 months will be recorded in CRF results. ** Performed in Institute of Pulmonology, EMPA of Pussia

** Performed in Institute of Pulmonology, FMBA of Russia.

Statistical Analyses.

Samples

Total set: all patients included in the study who have signed Informed Consent Form for participation in the study. All AEs including those occurred prior to the study therapy will be considered throughout the study for this sample.

Safety population: all patients who received at least one dose of the study drug. This sample will be used to *analyze the study treatment safety and tolerability*, since all the AEs identified after the study drug administration will be recorded.

Full Analysis Set. This sample includes all enrolled and randomized patients, except for those who met at least one of the following criteria:

- 1) non-compliance with inclusion / exclusion criteria;
- 2) the patient has not taken as minimum a single dose of the study drug;
- 3) lack of any data of the patient following randomization;

This sample is the most consistent with the "Intention-to-treat" principle, will be used for the *Intention-to-treat analysis (ITT analysis) of the the study therapy efficacy*.

Per protocol set. This sample includes all patients who completed the therapy as per the study protocol without any missing visits or significant protocol deviations. This sample will be used for the *Per Protocol analysis (PP- analysis) of the the study therapy efficacy*.

Mean value of the total set for the relevant day will be used to fill lacking/missing data.

Data treatment and all statistical calculations under the protocol will be made using SAS-9.4 statistical software⁴.

Evaluation of sample size

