- 1. To assess the dynamics of the compared indicators Friedman test, non-parametric analogue of analysis of variance with repeated measures.
- 2. For the frequency analysis of 2×2 cross tables $-\chi^2$ -test (if the compared frequencies are greater than 5) or Fisher exact test (if one of the compared frequencies is less than 5).
- 3. For the frequency analysis of cross tables with independent strata Cochran–Mantel– Haenszel test.
- 4. For the frequency analysis of data on the presence / absence of an event or outcome during repeated measures (cross tables with dependent strata) survival analysis.

To perform the above-mentioned non-parametric statistical analysis options, it is assumed that the following SAS procedures are used:

- FREQ Friedman test, χ^2 -test and / or Fisher exact test; Cochran–Mantel–Haenszel test
- LIFETEST survival analysis
- NPAR1WAY Mann-Whitney U-test.

Safety parameters

Adverse events recorded during the study will be grouped into frequency tables by severity, seriousness and relationship with the study drug.

Data presentation

Descriptive statistics will be provided for each study continuous / interval variable. Statistic data will be presented by mean, standard deviation, min and max values. Comparisons suggesting statistical conclusion will have the relevant confidence intervals. Outliers will be analyzed individually. The data will be grouped by visits. The categorical variables will be presented as frequency tables by visits.

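### No test is tied to the primary responder endpoint; the implied unadjusted chi-square test is valid, but naming one baseline-adjusted analysis could add precision at almost no cost

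*Combined protocol and SAP*

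**What the plan says.** All places are in the combined protocol and SAP.

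- **Endpoints.** The primary endpoint is binary: "response criterion is the reducing of the Total Cough Severity Score" by at least 1 point from baseline at week 4. Secondary endpoint 1 is "Severity of cough (TCSS according to the Cough Severity Scale) after 4 weeks of the treatment compared to baseline". Secondary endpoint 3 is "The severity of the clinical symptoms of COPD (according to COPD Assessment Test [CAT]) after 4 weeks of the treatment", with no mention of baseline.
- **Schedule of study procedures.** "Evaluation of cough severity (according to Cough Severity Scale") is marked at Visit 1 and Visit 2. CAT is marked at both visits too.
- **Evaluation of sample size, item 1.6.** The null hypothesis is p1 = p2, where p1 is the "proportion of subjects in Product group with improvement" of at least 1 point and p2 is its placebo counterpart. The sizing formula has no covariate or stratum term.
- **Non-parametric criteria.** The list opens with "Below, there are the main types of possible comparisons with the respective criteria". Item 2, "For the frequency analysis of 2×2 cross tables", gives the chi-square or Fisher test. Item 3 gives Cochran-Mantel-Haenszel for stratified tables but names no strata. Item 1 gives Friedman for change over time. The Mann-Whitney test appears among the SAS procedures.
- **Parametric criteria.** A Student t-test compares two groups on continuous variables, after a Kolmogorov-Smirnov check. ANCOVA is listed only in repeated-measures form. Non-normal data go to generalized or mixed linear models, with AIC guiding their specification, while the opening of Statistical criteria sends the same data to non-parametric tests.
- **Samples.** The full analysis set and the per-protocol set are both assigned to efficacy. Neither is named as the basis for the primary conclusion.

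**The concern.** The primary conclusion should rest on one test fixed in advance. Here it has to be inferred from a list. The most natural inference, chi-square on a 2×2 table, makes no use of baseline TCSS beyond its part in defining who responds. If patients who start with worse cough are more likely to gain a point, part of the variation in response is explained by a number already in the database, and adjusting for it narrows the interval for p1 − p2.

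The score endpoints have a related problem. The method follows from a normality check on the trial data, and the non-normal branch offers several methods. At stake are some precision and some analyst choice after the data are seen. The validity of the trial is not at stake.

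**Working it through.** **1. The plan's own figure.** Inputs from Evaluation of sample size: two-sided alpha 0.05, power 0.80, difference 0.20, ratio 1:1, largest sample size for that difference. The largest size falls at 0.6 versus 0.4.

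n = (1.960 + 0.842)² / 0.20² × (0.6×0.4 + 0.4×0.6) = 7.85 / 0.04 × 0.48 = 94.2, so 95 per arm. Withdrawals: 190 / 0.8 = 237.5, so 238. Both figures reproduce.

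**2. Is the implied test sound?** The smallest anticipated cell is 0.4 × 95 = 38, so the rule in item 2 selects chi-square and not Fisher. By exact binomial enumeration at 95 per arm, its two-sided size is 4.85% to 5.03% for response rates of 0.2 to 0.8, and its power at 0.6 versus 0.4 is 79.3%. It is valid and performs as planned.

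**3. What adjustment could add to the primary test.** The documents give no distribution for baseline TCSS and no correlation with week 4. Assumptions: integer scores, baseline mean 4 or 5, SD 1.5 or 2, truncated to 2–12; week-4 score linear in baseline, rounded and held within 0–12; response rates calibrated to 0.4 and 0.6; 95 complete cases per arm; 10,000 trials per scenario (Monte Carlo error about 0.4 points). The adjusted analysis is a logistic regression of response on treatment and baseline TCSS. Each patient's response probability is predicted under both arms and the average difference taken, with the corrected robust standard error described in the fix.

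| Assumed correlation | Chi-square power | Adjusted power | Gain (points) | Variance ratio, adjusted / unadjusted |
|---|---|---|---|---|
| 0.5 | 78.9–79.9% | 85.4–86.0% | 6.1–7.1 | 0.847–0.854 |
| 0.7 | 78.4–79.3% | 82.2–83.0% | 3.5–4.0 | 0.910–0.918 |
| 0.85 | 78.9–79.6% | 81.1–81.4% | 1.7–2.3 | 0.954–0.958 |
| Change unrelated to baseline | 79.0 and 79.6% | 79.0 and 79.5% | 0 | – |

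A separate run of 3,000 trials per scenario gave 80.3/86.6%, 80.1/83.5% and 78.1/78.9% at the three correlations, and 80.4/80.1% with change unrelated to baseline. Together the gain is about 1 to 7 points, or nil. The variance ratios equate to between 95 / 0.958 = 99 and 95 / 0.847 = 112 patients per arm analysed by chi-square.

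Type I error over 28 null scenarios was 4.4–5.3% for chi-square and 4.7–5.4% for the adjusted test. Mean 95% interval half-width was 0.139 unadjusted, 0.128–0.137 adjusted, and 0.140 adjusted when baseline is uninformative.

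**4. Scores.** With equal SD σ at both visits, correlation r and n per arm, the variance of the treatment difference is:

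- t-test on change: 4σ²(1 − r)/n
- ANCOVA: 2σ²(1 − r²)/n

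The ratio of ANCOVA to change is (1 − r²) / [2(1 − r)] = (1 + r)/2, which is 0.75, 0.85 and 0.925 at r = 0.5, 0.7 and 0.85. ANCOVA variance is therefore 25%, 15% and 7.5% smaller. In the simulated TCSS data, power was 91–98% for ANCOVA, 89–93% for a t-test on change and 87–93% for Mann-Whitney on change.

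**5. The normality check.** At 95 per arm, simulated integer TCSS failed the Lilliefors form of the Kolmogorov-Smirnov test in every sample, so TCSS would land in the branch that offers several methods. A wider integer score (assumed SD 5 to 8, as CAT might be) failed in at least one arm in 53% to 25% of trials, so there the sample would decide the method.

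**The case against.** The strongest reply is that nothing here is wrong. The implied test is valid, its power is as planned, and the benefit of adjustment rests on figures that no section supplies. In the main simulation a correlation below 1 makes patients with high baseline scores improve more, so baseline predicts response by construction. Where that link is removed, the gain vanishes. All of this stands, and it limits the point to an improvement.

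Several stronger readings are tempting, and the documents do not support them:

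- **Baseline TCSS goes unused.** It does not; it defines response. It is only not named as a covariate or stratum.
- **The plan rules out adjustment.** It lists generalized linear models with a choice of distribution, and Cochran-Mantel-Haenszel. It only fails to say which covariate or stratum would be used, and for which endpoint.
- **CAT would be compared without its baseline.** The endpoint wording allows that. However, the repeated-measures ANOVA in the plan, with two visits, amounts to a t-test on change and does use baseline. The larger variance reductions against a week-4 t-test (1 − r² gives 25%, 49% and 72% smaller at r = 0.5, 0.7 and 0.85) apply only if CAT is compared on the week-4 score alone.
- **No comparison of arms exists for non-normal scores.** Mann-Whitney is listed.
- **The gain also holds under the plan's missing-data rule.** The rule is "Mean value of the total set for the relevant day will be used to fill lacking/missing data". Filling week-4 TCSS with one mean makes a filled patient's response depend entirely on baseline, which creates an association. Even with change unrelated to baseline, it gave 68.7% unadjusted and 72.1% adjusted. It is not evidence for adjustment, and the figures in the table are for complete cases.

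Finally, the document calls itself a protocol summary, so fuller specification may exist elsewhere. The point concerns this document.

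**Conclusion.** The point holds as a cheap improvement; the plan is not wrong as written. No test, covariate, stratum or primary analysis set is fixed for the primary endpoint. The natural reading is a chi-square test that is valid and adequately powered.

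Adjusting for baseline TCSS would add about 1 to 7 power points at assumed correlations of 0.85 down to 0.5, and nothing if response is unrelated to baseline. For the scores, the gain of ANCOVA over a t-test on change depends only on the assumed r and on equal SDs at the two visits. Naming one method per endpoint is worthwhile even if adjustment gains nothing, because it removes a choice otherwise made after seeing the data. Confidence is medium, because the size of the gain cannot be fixed from the documents.

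**What to change.** Before unblinding, amend Statistical criteria as follows.

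1. **Primary endpoint.** Logistic regression of response on treatment and baseline TCSS, on one named primary analysis set, with its missing-data handling stated. Report the standardised risk difference, which targets the same p1 − p2 as Evaluation of sample size. Take the 95% interval and two-sided test from the robust (influence-function) standard error multiplied by √(n/(n − 3)), with a t quantile on n − 3 degrees of freedom, where n is the number of patients analysed. Keep chi-square as sensitivity analysis.
2. **TCSS and CAT scores.** Replace the normality check with ANCOVA of the week-4 score on treatment and the same score at baseline. Use Mann-Whitney on change as sensitivity analysis. This is a different form from the repeated-measures ANCOVA now listed.
3. **Friedman.** State that it is not used to compare arms; with two visits it tests only change within patients.

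Cost: a documented change to the statistical text, with no new patients, visits or data, and no change to the sample size. The primary estimate becomes model-based instead of being read from a 2×2 table, and the interval half-width grows by about 0.001 (0.140 instead of 0.139) if baseline proves uninformative.
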